Depressive disorders are common mental conditions with a prevalence of about 17% in urban UK (Ayuso-Mateos, 2001). The impact of depression on social, occupational and physical health and mortality is substantial. Depression causes a greater impairment in health state than the major chronic physical illnesses such as angina, arthritis, asthma, and diabetes. Although evidence based treatments for depression exist in the form of anti-depressant medication and cognitive behaviour therapy (CBT), there is much room for improvement. Remission rates are 43% for antidepressants and 29% for placebo (Gibbons et al, 2012). Even fewer patients will sustain response in the long-term. Response rates using CBT are generally equivalent to antidepressant medication (Amick et al, 2015). Efficacy of CBT in a meta-analysis was a modest $d=0.42$ after the effect of publication bias was removed (Cuijpers, 2010). There is little enthusiasm amongst pharmaceutical companies to develop new anti-depressant medications that would then compete with cheaper generic drugs. Psychological therapies have reached a plateau and newer developments focus on more efficient ways of delivering therapy (e.g. computerised CBT). A significant additional problem is that the response for any established treatment of depression may not occur for 6 weeks or more. There is some research in evaluating newer compounds such as intravenous ketamine. However, this requires a hospital setting, may have significant adverse effects and would be unacceptable to many patients.

One of the most rapid anti-depressants known is a night of total sleep deprivation (or “wake therapy”) (Benedetti & Colombo, 2011); up to 60% of patients respond by the next day with a 50% reduction on the Hamilton Rating Scale for depression and a final score of <9 (Gillin et al 2001). However, there is a very high rate of relapse amongst responders. Several combination strategies have been used in pilot studies to augment and maintain the rapid response after wake therapy. These have included adding daily bright “light therapy” in the morning and advancing the sleep phase for 3 days after sleep deprivation (“wake therapy”) (the combination is called “triple chronotherapy”) which has resulted in long-term maintenance of response in 3 RCTs. For example, Wu et al (2009) randomly assigned 49 bipolar inpatients with depression to triple chronotherapy, as an adjunct to medication, or to a medication-only group. Significant decreases in depression were found on day 2 in the triple chronotherapy group compared to treatment as usual. This was maintained over 7 weeks. Martiny et al (2012, 2013, 2015) randomly allocated 75 inpatients with non-seasonal unipolar depression on an anti-depressant (duloxetine) to either triple chronotherapy or to daily exercise for 5 days. (Sleep deprivation in this study consisted of a variation of three alternate nights of being awake). The triple chronotherapy was superior to exercise at Day 2-7 with a large effect size of 1.45. This is a larger effect size than medication or CBT and acted within 5

days. It was maintained at 6 month follow up, when the remission rate was 61.9% in the triple chronotherapy group compared to 37.9% in the exercise group. Lastly, Neumeister et al (1995) recruited 20 non-seasonal depressed in-patients on medication. They all received Partial Sleep Deprivation (sleep from 9:30 to 1am) and were then randomly allocated to either Bright Light or Dim Light. Patients receiving Bright Light did significantly better than those on Dim Light from Day 2 to 7. All three RCTs have small numbers and therefore the effect size may be exaggerated. There are also several open label case series of triple chronotherapy in both unipolar depression (for example Sahlem, 2014; Moscovici & Kotler, 2009) and bipolar disorder (Bendetti et al, 2005). Triple chronotherapy has so far been conducted in in-patients although one group has demonstrated the feasibility in a case series of 27 non-medicated out-patients with major depression in the Netherlands (Dallaspezia, 2016). These patients were supported during the night to stay awake. The Beck Depression Inventory score reduced from a mean of 25.8 (SD 7.7)(moderate range) to 13.7 (SD 7.7) (mild range) at one week and to 11.8 (SD 10.2) (mild range) at 3 months.

In the UK, the large majority of patients with depression in the NHS are treated in the community and are only admitted to hospital if there is a severe risk of suicide or self-neglect that cannot be managed in the community. Psychological treatment as usual usually consist of behavioural activation delivered by Psychological Well-Being Practitioners (PWPs) in the Improving Access to Psychological Therapies service and/or anti-depressant medication. Thus, one of the major objectives of the study one is to determine if triple chronotherapy is a practical treatment in the community. We will also focus on patients with unipolar depression, as this is far more common than bipolar. Our study will therefore be a randomised controlled trial that is designed as a feasibility study to answer the question whether Triple Chronotherapy enhances standard treatment of care for depression after 1 week and whether this is maintained at follow up.

Rationale: **There are no major breakthroughs on the horizon in the field of pharmacotherapy or psychotherapy for the rapid treatment of depression (within one week) without any significant side effects, so this is a novel approach. Triple chronotherapy is a term used to describe a combination of total sleep deprivation, followed by advance of sleep cycle and bright light therapy. Three small RCTs suggest that this is a promising treatment for the rapid treatment of depression. In addition, depression is a heterogeneous condition and this study has the potential in a larger trial to be part of a paradigm shift to determine subtypes of depression that may determine the type of treatment offered.**

Trial Objectives and Design

Our objective is to determine the feasibility of conducting a larger randomized controlled trial (RCT) of triple chronotherapy in a community sample of patients with depression, and enable us to determine

- 1) agreement to be randomised.
- 2) whether clinicians can recruit participants.
- 3) estimates of participant flow.
- 4) the feasibility of delivering the intervention in the community.
- 5) adherence to the protocol.

Aims: To conduct a double blind RCT comparing adding triple chronotherapy to standard treatment of care. Both groups will receive standard treatment as usual (TAU).

We hypothesise that:

- 1) Triple chronotherapy (Total Sleep Deprivation, Phase Advance and Bright Light Therapy) with standard care will be more effective than the control treatment with standard care on the Hamilton Depression Rating Scale (6 item) at 1 week.
- 2) The superiority of Triple Chronotherapy over the control treatment will be maintained at follow up at 2, 4, 8 weeks and at 6 months.

3.1.1 *Primary endpoints*

Our outcome measures are

- 1) agreement to be randomised.
- 2) whether clinicians can recruit participants.
- 3) estimates of participant flow.
- 4) the feasibility of delivering the intervention in the community.
- 5) adherence to the protocol.

[figure not shown]
3.1.2 *Secondary endpoints*

We will explore the means and SDs of the 6 item Hamilton Depression Rating Scale (Bech, 1981; O'Sullivan, 1997) outcomes to help inform the power analysis for a larger RCT.

Trial Design

This is a randomised parallel group single blind design. We will evaluate adding either Triple Chronotherapy or a control treatment to standard care. This design aims to show that we are able to recruit participants and that participants are able to adhere to the interventions. We will explore whether Triple Chronotherapy plus treatment as usual is more effective than treatment as usual on the HDRS (6 item).

Trial Flowchart

	Screen Visit	Visit 2 re-baseline before intervention	Visit 3 (1 week follow up)	Visit 4 (2 weeks follow up)	Visit 5 (4 weeks follow up)	Visit 6 (8 weeks follow up)	Visit 7 (6 month follow up)
Patient information and informed consent	X						
Intervention		X					
Outcome measures (observer rated rating scale)	X	X	X	X	X	X	X
Self-report outcome measures	X	X	X	X	X	X	X
Actigraphy and sleep diary	X		X				

4. Trial Intervention

Intervention Details

All participants who provide informed consent to participate will be randomised to receive either Triple Chronotherapy or a Control Treatment. Both groups will receive treatment as usual.

1) Triple Chronotherapy

This consists of (a) *Total Sleep Deprivation* with group support on days one and two; (b) *Phase Advance of Sleep* over 5 days and daily Light Therapy. On Day 1 (e.g. Monday), patients are supported in a group to stay up all night. We will arrange various activities to help patients stay awake accompanied by a Health Care Assistant (HCA) at the Hospital (e.g. watch a film; exercise; receive information on sleep hygiene; listen to music; short walk) and have access to coffee/ tea and snacks.

The next step is to *advance the phase of sleep*. Patients are helped to stay awake on Day 2 (Tuesday) at the hospital. They will either be collected by a relative or sent home by a taxi to go to bed at about 5pm. They should not drive or operate machinery. They wake by about 1am and will be invited to come to the hospital with support by a HCA in a group to stay awake. They will leave to go home by about 8am. They will then go to bed on Day 3 (Wednesday) at about 7.30pm. They will be asked to sleep until 3am. No further support is provided by the Hospital to stay awake at night. They then go to bed on Day 4 (Thursday) from 9.30pm to 5am and on Day 5 (Friday) at 11pm to resume a normal sleep routine waking by 6.30 to 7am. They will be given an information leaflet on sleep hygiene and given the opportunity to ask questions.

(c) *Bright Light Therapy* is given on Day 2 onwards daily. This is provided by a Carex Day Classic Light. The time of the therapy is optimised in the morning according to the patient's pattern of sleep. A patient sits about one foot away from a bright light box, that emits 10,000 Lux. It is positioned slightly above the head and pointing downwards at 45 degrees. Patients are free to have breakfast, read or use a computer while facing towards the light. Treatment normally last 30 minutes or more and will continue for 6 months. Possible side effects in the triple chronotherapy group include tiredness after sleep deprivation. A few people may experience nausea or headache after beginning light therapy. (In healthy individuals bright light therapy was not associated with any significant difference in side effects compared to dim light therapy (Botanov, 2013). However, patients with any significant side effects may be asked to reduce the exposure time by 10 minutes. Active treatment may theoretically trigger a manic episode, but patients with bipolar disorder are excluded and so this should be rare. We will however warn the patient and carer of this rare possibility. Patients may also receive standard care.

2) Control treatment

Participants will be given information on sleep hygiene and getting a good night's sleep in a written leaflet and given the opportunity to ask questions. They are then given SomniLight Amber Light daily for 1 week. Like the Bright Light Therapy, the timing is optimised in the morning according to the patient's pattern of sleep. A patient sits about one foot away from a light box, which is positioned slightly at 45 degrees above the head and pointing downwards. Patients are free to have breakfast, read or use a computer while facing towards the light. Treatment normally last 30 minutes.

The frequency of any side effect from either group will be monitored and clinicians would continue with treatment as usual. Participants with any significant side effects will be withdrawn, but included in the analysis.

Frequency and duration of intervention

The duration of the intervention is 1 week.

Intervention records

Therapy sessions (e.g wake therapy or sleep hygiene information) will be recorded in ePJS hospital records.

Subject Compliance.

Compliance to the intervention will be monitored and documented by the Health Care Assistant.

Study adherence

Participants will be encouraged to stay up during sleep deprivation as described above.

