Primary Efficacy Parameter To compare the rate of recruitment and adherence to the treatments in both groups	Number of participants recruited per month Adherence to the protocol This includes the number of length of naps in the active intervention.	At Week 1 At Week 1
Secondary Efficacy Parameter To compare the effects of the following measures in both groups 1) Hamilton Depression Rating Scale 2) Clinical Global Impression and Improvement Scale (Guy, 1976) 3) Quick Inventory of Depressive Symptomatology – SR version (Triveni et al, 2004). 4) Brief Ruminative Response Scale (Topper et al, 2014). 5) Pittsburgh Sleep Index (Bysse et al, 1999) 6) Euroquol 5D (EQ5-D) (1990). 7) Wrist actigraph from GeneActiv daily for 3 days pre-randomisation and 7 days post-randomisation. 8) Sleep diary daily for 3 days pre-randomisation and 7 days post-randomisation. 9) The credibility of the intervention and expectation of whether their mood will improve rapidly (Devilly, 2000). 10) Amount of anti-depressant drugs (in mg of anti-depressant equivalents) (Hayasaka et al, 2015) or	An observer rated measure of depression An observer rated measure of global severity A subjective measure of depression A measure of ruminative style A measure of sleep disturbance A measure of quality of life A measure of the sleep/wake activity, which correlates with the gold standard of sleep physiology (polysomnography). A subjective measure of total sleep time A measure of the credibility of the intervention Any additional treatment received	Baseline, rebaseline and at 1, 2, 4, 8 weeks and 6-month post-randomisation. Baseline, rebaseline and at 1, 2, 4, 8 weeks and 6-month post-randomisation. Baseline, rebaseline and at 1, 2, 4, 8 weeks and 6-month post-randomisation. Baseline, and at 1, 2, 4, 8 weeks and 6-month post-randomisation. Baseline, and at 1, 2, 4, 8 weeks and 6-month post-randomisation. Baseline, and at 1, 2, 4, 8 weeks and 6-month post-randomisation. Baseline, and at 1 week post-randomisation. Baseline, and at 1 week post-randomisation Baseline Baseline, and at 1, 2, 4, 8 weeks and 6-month post-randomisation

benzodiazepine drugs (in mg of diazepam equivalents 11) The amount of Cognitive Behaviour Therapy or any other counselling or psychotherapy (number of hours) 12) Reported side effects at 1 week.	Any additional treatment received Any reported side effects	Baseline, and at 1, 2, 4, 8 weeks and 6-month post-randomisation At 1, 2, 4, 8 weeks and 6-month post
--	--	--

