The trial may be prematurely discontinued by the Sponsor or Chief Investigator on the basis of new safety information or for other reasons given by the regulatory authority or ethics committee concerned.

The trial may also be prematurely discontinued due to lack of recruitment. If the study is prematurely discontinued, active participants will be informed and no further participant data will be collected.

10. Statistics

Sample Size

N=30 equally randomized to each group is usually adequate for a feasibility study exploring the rates of recruitment and attrition (Browne, 1995). We will explore the data for an estimate of effect size to determine consistency with previous studies.

Randomisation

The method of randomisation will consist of simple randomisation based on a constant allocation ratio of 1:1. It will be stratified according to the season.

Analysis

We will explore the means and SDs of outcomes to help inform the power analysis for a larger RCT of clinical and cost effectiveness of adding triple chronotherapy in depression. Follow-up will be maximised to prevent missing data by reminding participants at each visit of the importance of collecting data. Participants will be telephoned when they do not provide follow up data. The reasons for missing data will be recorded. Missing data for the primary outcome will be handled by multiple imputation to estimate missing outcome data. The self-report depressive symptom measures will be used in the imputation process.

11. Trial Steering Committee

There is no trial Steering Committee as this is a feasibility study with no significant risks.

12. Data Monitoring Committee

There is no Data Monitoring Committee as this is a feasibility study with no significant risks.

13. Direct Access to Source Data and Documents

The Investigator(s) will permit trial-related monitoring, audits and REC review by providing the Sponsor(s), and REC direct access to source data and other documents (eg patients' case sheets, blood test reports, X-ray reports, histology reports etc).

14. Ethics & Regulatory Approvals

The trial will be conducted in compliance with the principles of the Declaration of Helsinki (1996), the principles of GCP and in accordance with all applicable regulatory requirements including but not limited to the Research Governance Framework.

This protocol and related documents will be submitted for review to XXXXXX Research Ethics Committee (REC)

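### The trial sets out to determine whether a larger RCT is feasible, but no primary endpoint has a pre-stated progression criterion, and the one stated primary analysis, a between-group comparison, does not answer that question.

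*Combined protocol and SAP*

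**What the plan says.** Under Trial Objectives and Design, the combined protocol and SAP states: "Our objective is to determine the feasibility of conducting a larger randomized controlled trial". Five items follow, and section 3.1.1 repeats them as the primary endpoints: "agreement to be randomised", "whether clinicians can recruit participants", "estimates of participant flow", "the feasibility of delivering the intervention in the community" and "adherence to the protocol". The Trial Design section adds that the design is meant to show that people can be recruited and can adhere.

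The table in section 8 (Assessment of Efficacy) gives the primary parameter as "To compare the rate of recruitment and adherence to the treatments in both groups". Its measures are participants recruited per month and protocol adherence, which includes naps in the active arm. Neither has a cut-off.

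Section 10 (Statistics) supports N=30 by citation. Its Analysis paragraph covers means, SDs and multiple imputation. It gives no analysis or decision rule for the five feasibility endpoints.

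The Stopping Rules in section 9 say: "The trial may also be prematurely discontinued due to lack of recruitment". No rate, number or date is attached.

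**The concern.** A trial that undertakes to determine and to show feasibility needs a stated standard for what would show it. Two of the five endpoints, whether clinicians can recruit and whether the intervention can be delivered in the community, are close to verdicts rather than measures and cannot be answered without a criterion.

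The one analysis that is stated does not supply that standard. Recruitment and agreement to be randomised precede the 1:1 allocation, so there is no recruitment rate by arm to compare. Adherence means different things in the two arms: a wake night followed by phase advance and bright light in one, a leaflet and amber light in the other. Similar rates could be similarly poor, and different rates would not settle whether the active treatment is deliverable.

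What is at stake is the trial's main conclusion. A threshold chosen after the rates are known cannot serve as a prespecified standard.

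**Working it through.** **Is there a decision figure to reproduce?** No. N=30 rests on a cited rule of thumb. The documents give no target rate, precision, power or planned monthly recruitment. The check is therefore a reading of the text, followed by an illustration.

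**Endpoint by endpoint**

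| Primary endpoint (3.1.1) | Measure given | Criterion given |
|---|---|---|
| Agreement to randomisation | None; counts of eligible patients who decline are to be reported (section 6) | None |
| Clinicians able to recruit | Participants per month (section 8) | None |
| Participant flow | CONSORT-style reporting of those not randomised (section 6) | None |
| Deliverability in the community | None | None |
| Adherence | Adherence at Week 1, including naps (section 8) | None; an adherent participant is not defined |

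**How much is left to judgement.** These are exact (Clopper-Pearson) 95% intervals for x successes in n. The lower limit is the 0.025 quantile of Beta(x, n−x+1) and the upper limit is the 0.975 quantile of Beta(x+1, n−x). The size of the active arm is 15 or 30, depending on whether N=30 is read as the total or as per group.

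- 12/15 (80%): 52% to 96%
- 24/30 (80%): 61% to 92%
- 21/30 (70%): 51% to 85%

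**What zones would do at this size.** The following thresholds are assumptions, not figures from the documents. For wake-night completion in the active arm, take go at 70% or more, amend at 50% to below 70%, and stop below 50%. With X ~ Binomial(n, p):

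- n=30: go is X ≥ 21 and stop is X ≤ 14.
- n=15: 70% of 15 is 10.5, so go is X ≥ 11; 50% is 7.5, so stop is X ≤ 7.

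| n | True rate | P(go) | P(amend) = 1 − P(go) − P(stop) | P(stop) |
|---|---|---|---|---|
| 30 | 50% | 0.021 | 0.551 | 0.428 |
| 30 | 70% | 0.589 | 0.405 | 0.006 |
| 15 | 50% | 0.059 | 0.441 | 0.500 |
| 15 | 70% | 0.515 | 0.434 | 0.050 |

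A poor true rate seldom passes, and an adequate one is seldom stopped. The middle zone is heavily used: a true 50% reaches stop only 43% to 50% of the time, and a true 70% reaches go only 52% to 59% of the time.

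**The case against.** The strongest reply is that this is an estimation study. The protocol speaks of estimating flow and exploring rates, never uses go/no-go language, and offers means and SDs for a later power calculation. Rates with intervals can inform a later decision without a formal rule. The data needed are largely planned: reporting of patients who were eligible but declined (section 6), compliance documented by the Health Care Assistant (section 4), nap, actigraphy and diary data (section 8), and reasons for missing data (section 10). Most of this stands. It means no new data collection is needed and that zones should not be presented as a hypothesis test. It does not rescue the between-group comparison, and it does not supply a standard for a protocol that also says it will determine and show feasibility.

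Several stronger readings are tempting but unsupported:

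- **That no result could lead to 'no'.** A missing cut-off does not rule out a negative judgement, and the recruitment clause shows that the sponsor contemplates failure. That clause is discretionary, has no figure, and concerns ending this trial rather than deciding on the next.
- **That all five endpoints are to be compared between arms.** The comparison wording covers only recruitment and adherence.
- **That the investigators would judge their own follow-on trial.** The documents do not say who decides. Section 14 sends the final report to the funder, the ethics committee and the sponsor.
- **That a simple rule separates good from bad rates at this size.** The table above shows only modest discrimination, and for one criterion alone.

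Finally, a figure directly after the endpoint list and some front pages could not be seen. Nothing in the remaining text refers to criteria held there, but the finding of absence is limited to the text supplied.

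**Conclusion.** The point holds in this form: in the supplied text no primary endpoint has a pre-stated progression criterion, the stated primary comparison does not address feasibility, and the recruitment stop has no figure. The change is worth making, because the gap affects the trial's main conclusion. It biases no estimate.

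Its size cannot be expressed as an error rate, because there is no rule to evaluate. The nearest measure is the width of the intervals, about 44 percentage points (52-96%) at 12/15 and 31 points (61-92%) at 24/30. The operating characteristics above rest on assumed thresholds, assumed true rates of 50% and 70%, independent participants, and 15 or 30 people in the active arm.

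**What to change.** In the section 8 table, replace the between-group comparison with single-rate estimates, each with an exact 95% CI:

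1. Proportion of eligible patients who agree to randomisation.
2. Participants randomised per month (a count over time, so an exact Poisson interval).
3. Proportion of the active arm completing the wake night, with 'completed' defined from the nap, actigraphy and diary data already collected.
4. Proportion with an HDRS-6 score at 1 week.

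Before any outcome summary is seen, fix go / amend / stop zones for each, with values chosen by the sponsor. State a planned monthly recruitment rate first; without it, neither a recruitment zone nor the lack-of-recruitment clause has a referent. State also that the zones guide the decision and are not a powered test, and say how the four combine if they disagree.

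The cost is protocol wording: no extra patients, visits or data items. The downside is that thresholds involve judgement and may return an unwelcome amend or stop.

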5.5 Concomitant Medication

A patient may be taking anti-depressant medication so long as the dose has been stable for 6 weeks and there are no plans to increase the dose or to alter the medication.

A wash out time for a patient deciding to stop anti-depressant medication and recruitment is 6 weeks. Surgery/radiotherapy is allowed after the first week of the intervention.

5. Research environment

This is a single centre trial at the South London and Maudsley NHS Foundation Trust. There are no specific site requirements. Recruitment will be from local GPs on the Clinical Research Network; Improving Access to Psychological Therapies (IAPT); clinicians on the Home Treatment Teams (secondary care) in Southwark, Lewisham, Lambeth and Croydon; through Consent for Contact on CRIS and on a dedicated website. For all settings, the intervention will be conducted at a hospital where support will be provided by a health care assistant for two nights and for one day to help patients stay awake (e.g. watch a film; exercise; short walk) and have access to coffee/ tea and snacks.

6. Selection and Withdrawal of Subjects

Inclusion Criteria

- 1) Diagnosis of Depressive Episode (ICD10 F32) or Recurrent Depressive Disorder (F33).
- 2) Minimum score of 8 or more on the Hamilton Depression Rating Scale (6 item) (Range 0-22) (Bech,1981). This represents at least moderate depression.
- 3) Age 18-65
- 4) Able to give informed consent
- 5) Women of child bearing age may be included and no methods of contraception is required to enable inclusion into the trial.

Exclusion Criteria

- 1) Current diagnosis of Seasonal Affective Disorder
- 2) Current diagnosis of anorexia nervosa or bulimia.
- 3) Current diagnosis of an obsessive compulsive or related disorder
- 4) Current diagnosis of post-traumatic stress disorder
- 5) History of schizophrenia, schizoaffective disorder or bipolar disorder
- 6) Severe cognitive impairment, dementia, intellectual disability or organic brain disorder.
- 7) History of stimulant or hallucinogenic misuse, alcohol or substance misuse or dependence in past 3 months.
- 8) Borderline Personality Disorder or other personality disorder considered to be the main problem.
- 9) Duration of depression more than 2 years.
- 10) Significant risk of suicide that requires hospitalisation.

- 11) Severe eye disease or cataracts or traumatic injury or visual impairment affecting both eyes.

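### Active-arm light is set at 6 months but the intervention at 1 week; the only listed adherence timepoint is Week 1, and no light-use measure is listed

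*Combined protocol and SAP*

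**What the plan says.** All references are to the combined protocol and SAP.

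- **Light, active arm** (section 4, Intervention Details, part c): bright light "is given on Day 2 onwards daily", and "Treatment normally last 30 minutes or more and will continue for 6 months".
- **Light, control arm** (section 4, Control treatment): "They are then given SomniLight Amber Light daily for 1 week".
- **Stated duration** (section 4, Frequency and duration of intervention): "The duration of the intervention is 1 week". The Trial Flowchart marks the intervention at Visit 2 only.
- **A hint that it lasts longer** (section 5.5, Concomitant Medication): "Surgery/radiotherapy is allowed after the first week of the intervention".
- **Adherence as an endpoint**: section 3.1.1 lists adherence to the protocol among the primary endpoints, without a time limit. Trial Design makes showing that participants can adhere one of its aims. The table in section 8 gives Week 1 as the timepoint and mentions naps in the active arm as something the measure includes.
- **Compliance records** (section 4): "Compliance to the intervention will be monitored and documented by the Health Care Assistant", and "Therapy sessions (e.g wake therapy or sleep hygiene information) will be recorded in ePJS hospital records". The Study adherence paragraph deals only with staying up during sleep deprivation.
- **Secondary measures** (section 8): none of the 12 records use of the light box. The sleep diary and actigraph are described as sleep measures, and their collection ends 7 days after randomisation. Drug dose and hours of psychological therapy are recorded at baseline, 1, 2, 4 and 8 weeks and 6 months.

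**The concern.** There are two linked problems. First, the protocol gives two durations and does not say how they fit together. A 1-week acute package followed by home light in the active arm is the most natural reading, but the reader has to infer it.

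Second, on that reading the longest component of the active treatment has no listed adherence measure. Adherence is one of the questions this feasibility study exists to answer. The background section presents daily morning light, combined with phase advance, as a way of holding on to the rapid response to wake therapy, and the second hypothesis is that superiority lasts to 6 months. The HDRS-6 means and SDs are meant to inform the power analysis of a larger trial. Without light-use data, the team could not tell from what is listed whether participants kept using the light at home, or what exposure the later HDRS-6 values reflect.

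**Working it through.** The plan states no figure for this point, so there is none to reproduce. The check sets the statements side by side and then counts days.

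**1. Which statements fit which duration?**

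| Statement | Fits 1 week | Fits 6 months |
|---|---|---|
| Bright light daily from Day 2, continuing 6 months (section 4) | no | yes |
| Intervention lasts 1 week (section 4) | yes | only if it means the acute package |
| Intervention marked at Visit 2 only (Flowchart) | yes | only if it means the start |
| Reference to a first week of the intervention (section 5.5) | possible | yes, more naturally |
| Adherence timed at Week 1 (section 8) | yes | covers only the start |

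Neither reading satisfies every line as written.

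**2. Is light use listed anywhere?** Adherence row in section 8: naps only. The 12 secondary measures: none. Session records: the examples are wake therapy and sleep hygiene. Study adherence paragraph: sleep deprivation only. Compliance sentence: general, with no light item, instrument or schedule. So light use is not specified in either arm, in Week 1 or later.

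**3. How much of a 6-month course lies beyond the listed timepoint?**

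Inputs:
- Light starts on Day 2 (section 4).
- Week 1 covers Days 2 to 7, which is 6 light days, or Days 2 to 8, which is 7 light days if Visit 3 falls 7 days after Day 1.
- Six months is taken as 168 light days (24 weeks) to 184. This is an assumption; the protocol gives no day count.

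Share of light days inside Week 1 = Week 1 light days / total light days:
- lowest: 6 / 184 = 3.3%
- highest: 7 / 168 = 4.2%

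Light days after Week 1 = total minus Week 1 light days:
- 168 − 7 = 161, and 161 / 168 = 95.8%
- 184 − 6 = 178, and 178 / 184 = 96.7%

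So about 96 to 97% of the prescribed active-arm light days come after the only listed adherence timepoint. This is overlap on the calendar. It does not mean that light use is measured for the remaining 3 to 4%, since no light item is listed for Week 1 either.

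**4. On the 1-week reading**, these percentages do not apply. What remains is unlisted light use in Week 1 and an incorrect 6-month sentence.

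**The case against.** The strongest reply is that the wording is open rather than restrictive. The adherence row says what the measure includes, not that naps are all of it. The session-record sentence gives examples. The Health Care Assistant's duty to document compliance covers the intervention as a whole, has no end date and is not confined to one arm. The Week 1 entry is also weak evidence of an exclusive window: the same entry times monthly recruitment, where Week 1 makes little sense, and section 3.1.1 sets no time limit. Finally, the 1-week duration, the single flowchart mark and the 1-week primary hypothesis agree with each other, so a one-sentence correction might be all that is needed.

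Much of this stands, and it rules out three stronger readings.

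- A reader might infer that adherence to 6 months of light could not be reported at all. The documents do not support that. It depends on the 6-month reading and on treating open wording as exhaustive. What can be said is that the listed data would not show it.
- A reader might infer that compliance monitoring stops when the Health Care Assistant's support stops, because "support will be provided by a health care assistant for two nights and for one day to help patients stay awake". That sentence describes help with staying awake and sets no limit on compliance monitoring, so no share of light days can be derived from it.
- A reader might infer that the follow-up comparison is biased because light continues in one arm and stops in the other. The arms can still be compared as assigned packages, and descriptive means and SDs can be calculated without exposure data.

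What the reply does not supply is a light-use item or a schedule for one. A general duty to document compliance does not ensure that home light use is recorded in a comparable form at 2, 4 and 8 weeks and 6 months.

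**Conclusion.** The concern holds in a bounded form. The conflict between 6 months and 1 week is certain from the text. It is also certain that no light-use measure is listed for either arm at any visit. The size depends on which duration is meant. If 6 months, and taking that as 168 to 184 light days, about 96 to 97% of prescribed active-arm light falls after the only listed adherence timepoint. The feasibility of 6 months of home light, and the exposure behind the later HDRS-6 summaries, would then be unknown from the listed data. If 1 week, the loss is confined to Week 1 light use. No effect on an estimate, an SD or the sample size has been shown. The point should be fixed because it concerns a primary feasibility endpoint, but the trial remains viable without the change.

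**What to change.** 1. State one light duration per arm and bring the paragraph on frequency and duration into line with it. For example: a 1-week acute package and then home light to 6 months in the active arm, with amber light for 1 week in control.
2. Add one short self-completed item (days the light was used, usual minutes) at Visits 3 to 7. Give it to both arms at every one of these visits, with zero an allowed answer, so that the forms do not differ by arm after control light has ended.
3. Keep the item from the HDRS-6 rater, for example by direct entry by the participant or a sealed return, and write this handling into the protocol.
4. Report light adherence for Week 1 and for each later interval separately.
5. If 1 week is meant for both arms, correct the 6-month sentence and use the item at Visit 3 only.

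The cost is protocol wording plus one item in the self-report set that the flowchart already schedules at Visits 3 to 7, so no visits are added. The downsides are slight participant burden, recall error in self-reported use, and a risk of unblinding if the rater sees the item.
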